7.1 Sponsor-Investigator Reporting Requirements

7.1.1 Reporting to the Human Research Protection Office (HRPO) at Washington University

Reporting will be conducted in accordance with Washington University IRB Policies.

Pre-approval of all protocol exceptions must be obtained prior to implementing the change.

7.1.2 Reporting to the Quality Assurance and Safety Monitoring Committee (QASMC) at Washington University

The Washington University Sponsor-Investigator (or designee) is required to notify the QASMC of any unanticipated problem involving risks to participants or others occurring at WU or any BJH or SLCH institution that has been reported to and acknowledged by HRPO. (Unanticipated problems reported to HRPO and withdrawn during the review process need not be reported to QASMC.)

QASMC must be notified within **10 days** of receipt of IRB acknowledgment via

email to [contact]. Submission to QASMC must include the myIRB form and any supporting documentation sent with the form.

For events that occur at secondary sites, the Washington University Sponsor Investigator (or designee) is required to notify the QASMC within 10 days of Washington University notification via email to [contact]. Submission to QASMC must include either the myIRB form and supporting documentation or (if not submitted to myIRB) the date of occurrence, description of the event, whether the event is described in the currently IRB approved materials, the event outcome, determination of relatedness, whether currently enrolled participants will be notified, and whether the informed consent document and/or any study procedures will be modified as a result of this event.

7.1.3 Reporting to Secondary Sites

The Washington University Sponsor-Investigator (or designee) will notify the research team at each secondary site of all unanticipated problems involving risks to participants or others that have occurred at other sites within **10 working days** of the occurrence of the event or notification of the Sponsor-Investigator (or designee) of the event. This includes events that take place both at Washington University and at other secondary sites, if applicable.

7.1.4 Reporting to the FDA

The conduct of the study will comply with all FDA safety reporting requirements. **PLEASE NOTE THAT REPORTING REQUIREMENTS FOR THE FDA DIFFER FROM REPORTING REQUIREMENTS FOR HRPO/QASMC.** It is the responsibility of the Washington University principal investigator to report any unanticipated problem to the FDA as follows:

- Report any unexpected fatal or life-threatening suspected adverse reaction (refer to Appendix B for definitions) no later than 7 calendar days after initial receipt of the information.
- Report a suspected adverse reaction that is both serious and unexpected (SUSAR, refer to Appendix B) no later than 15 calendar days after it is determined that the information qualifies for reporting. Report an adverse event (refer to Appendix B) as a suspected adverse reaction only if there is evidence to suggest a causal relationship between the drug and the adverse event, such as:
 - A single occurrence of an event that is uncommon and known to be strongly associated with drug exposure
 - One or more occurrences of an event that is not commonly associated with drug exposure but is otherwise uncommon in the population exposed to the drug
 - An aggregate analysis of specific events observed in a clinical trial that indicates those events occur more frequently in the drug treatment group

- than in a concurrent or historical control group
- Report any findings from epidemiological studies, pooled analysis of multiple studies, or clinical studies that suggest a significant risk in humans exposed to the drug no later than 15 calendar days after it is determined that the information qualifies for reporting.
- Report any findings from animal or in vitro testing that suggest significant risk in humans exposed to the drug no later than 15 calendar days after it is determined that the information qualifies for reporting.
- Report any clinically important increase in the rate of a serious suspected adverse reaction of that listed in the protocol or IB within 15 calendar days after it is determined that the information qualifies for reporting.

Submit each report as an IND safety report in a narrative format or on FDA Form 3500A or in an electronic format that FDA can process, review, and archive. Study teams must notify the Siteman Cancer Center Protocol Development team of each potentially reportable event within 1 business day after initial receipt of the information, and must bring the signed 1571 and FDA Form 3500A to the Siteman Cancer Center Protocol Development team no later than 1 business day prior to the due date for reporting to the FDA.

Each notification to FDA must bear prominent identification of its contents (“IND Safety Report”) and must be transmitted to the review division in the Center for Drug Evaluation and Research (CDER) or in the Center for Biologics Evaluation and Research (CBER) that has responsibility for review of the IND. Relevant follow-up information to an IND safety report must be submitted as soon as the information is available and must be identified as such (“Follow-up IND Safety Report”).

7.1.5 Reporting to Merck & Co., Inc.

The WU PI shall forward to Merck’s Global Safety group ([contact]) any SAE and SUSAR information, including, but not limited to, all initial and follow-up information involving any study subject in the study within 24 hours (whichever comes first) of learning of the SAE or SUSAR.

“Adverse Event” or “AE” shall mean any untoward medical occurrence in a Study subject who is administered the Study Drug regardless of whether or not a causal relationship with the Study Drug exists. By way of example and without limitation, an AE can be any unfavorable and unintended sign (for example, an abnormal laboratory finding), symptom, or disease temporally associated with the use of the Study Drug.

“Serious Adverse Event” or “SAE” shall mean any untoward medical occurrence in a Study subject who is administered the Study Drug that results in death, a life-threatening drug experience, requires inpatient hospitalization or prolongation of existing hospitalization, results in persistent or significant disability/incapacity, or

is a congenital anomaly/birth defect, cancer, or is a new cancer if the cancer is the condition of the study, or overdose. Other important medical events that may jeopardize the patient or may require intervention to prevent one of the outcomes listed previously should also be considered “serious.”

“Suspected Unexpected Serious Adverse Reaction” or “SUSAR” shall mean any Serious Adverse Event, the nature, severity or frequency of which is not consistent with information in the most current investigator’s brochure, or with respect to a marketed product the most current Summary of Product Characteristics (SPC) or Package Insert.

7.1.5.1 Reporting Overdose

For purposes of this trial, an overdose of pembrolizumab will be defined as any dose of 1,000 mg or greater (≥ 5 times the indicated dose). No specific information is available on the treatment of overdose of pembrolizumab. Appropriate supportive treatment should be provided if clinically indicated. In the event of overdose, the subject should be observed closely for signs of toxicity. Appropriate supportive treatment should be provided if clinically indicated.

If an adverse event(s) is associated with (“results from”) the overdose of a Merck product, the adverse event(s) is reported as a serious adverse event, even if no other seriousness criteria are met.

If a dose of Merck’s product meeting the protocol definition of overdose is taken without any associated clinical symptoms or abnormal laboratory results, the overdose is reported as a non-serious Event of Clinical Interest (ECI), using the terminology “accidental or intentional overdose without adverse effect.”

All reports of overdose with and without an adverse event must be reported within 24 hours to the Sponsor and within 2 working days to Merck Global Safety. (Attn: Worldwide Product Safety; [contact])

7.1.5.2 Reporting Events of Clinical Interest

Selected non-serious and serious adverse events are also known as Events of Clinical Interest (ECI) and must be reported within 2 working days to Merck Global Safety by the WU PI. (Attn: Worldwide Product Safety; [contact])

Events of clinical interest are defined in Appendix B.

7.1.5.3 Reporting Pregnancy and Lactation

Although pregnancy and infant exposure during breastfeeding are not considered adverse events, it is the responsibility of investigators or their designees to report any pregnancy or lactation in a subject (spontaneously reported to them) that occurs during the trial.

Pregnancies and infant exposures during breastfeeding that occur after the consent form is signed but before registration must be reported by the investigator if they cause the subject to be excluded from the trial, or are the result of a protocol-specified intervention, including but not limited to washout or discontinuation of usual therapy, diet, placebo treatment or a procedure.

Pregnancies and infant exposures during breastfeeding that occur from the time of registration through 120 days following cessation of Sponsor's product, or 30 days following cessation of treatment if the subject initiates new anticancer therapy, whichever is earlier, must be reported by the investigator. All reported pregnancies must be followed to the completion/termination of the pregnancy. Pregnancy outcomes of spontaneous abortion, missed abortion, benign hydatidiform mole, blighted ovum, fetal death, intrauterine death, miscarriage and stillbirth must be reported as serious events (Important Medical Events). If the pregnancy continues to term, the outcome (health of infant) must also be reported.

Such events must be reported within 24 hours to the Sponsor and within 2 working days to Merck Global Safety. (Attn: Worldwide Product Safety; [contact])

7.2 Reporting Requirements for Secondary Sites

The research team at each secondary site is required to promptly notify the Washington University Sponsor-Investigator and Designee of all serious adverse events (Refer to Appendix B) within **1 working day** of the occurrence of the event or notification of the secondary site's PI of the event. This notification may take place via email if there is not yet enough information for a formal written report using a FDA form 3500a (MedWatch form) and Washington University cover sheet (Appendix D). A formal written report must be sent to the Washington University Sponsor-Investigator within **4 calendar days** (for fatal or life-threatening suspected adverse reactions) or 11 calendar days (for serious unexpected adverse reactions) of the occurrence of the event or notification of the secondary site's PI of the event.

The research team at a secondary site is responsible for following its site's guidelines for reporting applicable events to its site's IRB according to its own institutional guidelines. The research team at Washington University is responsible for reporting all applicable events to the FDA and Merck & Co. as needed.

Washington University pre-approval of all protocol exceptions must be obtained prior to implementing the change. Local IRB approval must be obtained as per local guidelines. Washington University IRB approval is not required for protocol exceptions occurring at secondary sites.

7.3 Exceptions to Expedited Reporting

Events that do not require expedited reporting as described in Section 7.1 include:

- Planned hospitalizations
- Hospitalizations < 24 hours
- Respite care
- Events related to disease progression

Events that do not require expedited reporting must still be captured in the EDC.

8.0 PHARMACEUTICAL INFORMATION

8.1 MK-3475

8.1.1 MK-3475 Description

MK-3475 is a potent humanized IgG4 mAb with high specificity of binding to the PD-1 receptor, thus inhibiting its interaction with PD-L1 and PD-L2. Based on preclinical in vitro data, MK-3475 has high affinity and potent receptor blocking activity for PD-1. MK-3475 has an acceptable preclinical safety profile and is being advanced for clinical development as an IV immunotherapy for advanced malignancies.

8.1.2 Clinical Pharmacology

Refer to Section 5.2 of the IB.

8.1.3 Pharmacokinetics and Drug Metabolism

Refer to Section 5.2 of the IB.

8.1.4 Supplier

MK-3475 will be provided free of charge by Merck & Co., Inc.

8.1.5 Dosage Form and Preparation

Merck will provide MK-3475 as a liquid drug product.

8.1.6 Storage and Stability

MK-3475 should be stored under refrigerated conditions (2°C - 8°C).

If not used immediately, vials and/or IV bags may be stored at 2-8 °C for up to a cumulative time of 20 hours. If refrigerated, the vials and/or IV bags should be allowed to equilibrate to room temperature prior to subsequent use. MK-3475 solutions may be stored at room temperature for a cumulative time of up to 4 hours.

8.1.7 Administration

MK-3475 will be given intravenously over the course of 30 minutes (-5 min/+10 min) on an outpatient basis.

8.1.8 Special Handling Instructions

No special handling instructions.

9.0 CORRELATIVE STUDIES

The collections for correlative studies are for patients enrolled in phase II only unless otherwise indicated.

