1.6 Correlative Studies Background

In both arms of phase II, intratumoral PD-L1 expression will be determined by qRT-PCR and/or IHC. TIL profile will be assessed by flow and mass spectrometry or IHC to compare to the profile at initial surgery prior to recurrence (when available). Glioma-specific immune response will be assessed in cultured TIL, peripheral blood, and sampled cLN (where available). Pre- and post-surgery peripheral blood will be assessed by flow cytometry through the Center for Human Immunology and Immunotherapy immune monitoring core (for Washington University samples) and the [name] lab or the University of Florida Brain Tumor Immunotherapy Program (for the UF samples) for markers of T cell activation and anergy as well as cytokine profiles. In addition, PD-1-dependent signature in glioma cell-specific T cells from the peripheral blood and sampled cLN where samples and RNAseq are available can be generated by novel RNAseq methodology developed at Washington University and University of Florida in order to characterize the PD-1-dependent transcriptional signatures and develop a PD-1 dependent biomarker program that will be easily de-convoluted to provide data on serial changes in (a) cell type composition and (b) cell type activation programs. Furthermore, if necessary, serum or plasma will be assessed for the presence and level of soluble immune checkpoint molecules, cytokines, and chemokines using commercially available multiplex immunoassays.

1.7 Rationale for Amendment 12

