9.1 Blood Specimens

9.1.1 Collection of Specimens

Forty mL of blood will be collected into 4 pink top tubes (with EDTA) for isolation of PBMCs at the following time points **for Phase II patients only**:

- No more than one week prior to surgical procedure (including resection/debulking, MLA or biopsy)
- No more than 3 days prior to the first dose of MK-3475
- No more than 7 days prior to the second dose of MK-3475 and at doses 4, 6, 9, 18, and 36
- At the end of treatment visit

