15.2 Analysis Plan

PFS and OS will be estimated by Kaplan-Meier product limit method and the difference in PFS with recurrent GBM being treated with MK-3475 alone vs. those being treated with MK-3475 plus MLA will be compared by log-rank test.

Two-group t-test will be used to compare the anti-glioma immune response before and after MK-3475 with or without MLA.

Cox proportional hazard model will be used to determine the relationship between intratumoral expression of PD-L1, the frequency of glioma cell-specific cytotoxic T cells with PFS and OS while proportional hazard assumption will be examined.

Pearson correlation coefficient (r) will be calculated between intratumoral expression of PD-L1 and the frequency of glioma cell-specific cytotoxic T cells. Similarly, Cox proportional hazard model will be used to investigate the relationship between PD-1-dependent biomarkers in glioma cell-specific T cells and PFS and OS.

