15.4 Interim Analysis

Per DSMC request, an interim analysis was conducted in June 2019. The MK-3475 + MLA group included 2 GBM patients who received 200mg in Phase 1 and 10 patients in Phase 2. PFS probability at 6, 9, and 12 months after treatment are 45.0%, 45.0%, and 33.8%, the median PFS is 5.49 months. Survival probabilities at 6, 9, and 12 months after treatment are 75.0%, 62.5%, and 50.0%, and the median OS is not estimable. For the MK-3475 monotherapy (no MLA) group, PFS probability at 3 months after treatment is 44.4%

and the median PFS is 2.73 months (95% CI: 1.41-3.88). Survival probabilities at 3 and 6 months after treatment are 83.3%, and 31.3%, and the median OS is 4.77 months (95% CI: 1.74-8.78).

This analysis showed significant differences in PFS and survival probabilities between the MK-3475 + MLA group and the MK-3475 alone group. Therefore, with Amendment 12, we are revising the study to a single arm (MK-3475 + MLA) in the spirit of minimizing harm, potential or perceived, to subjects and to complete the study in a timely manner. The recent study⁴⁶ shows median PFS was 2.4 months. To be conservative, we will use the shorter mPFS for MK-3475 + MLA group and longer mPFS from historical data. We will enroll additional 27 patients and expect 20 GBM patients will be evaluable for this study. With an accrual interval of 20 months and additional follow-up of 6 months, a two-sided, one-sample logrank test calculated from a sample of 32 subjects achieves 80.9% power at a 0.05 significance level to detect a median PFS of 5.1 months in the MK-3475 + MLA group when the median PFS of the historical control is 2.9 months.

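### The biomarker Cox models in Section 15.2 carry no treatment group although both phase II arms supply samples, so for markers measured after MLA they mix the MLA effect with the marker effect

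*Combined protocol and SAP*

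**What the plan says.** **Who is sampled.** Section 9.0: "The collections for correlative studies are for patients enrolled in phase II only unless otherwise indicated". That sentence limits collection by phase, not by arm. Section 1.6 is explicit: "In both arms of phase II, intratumoral PD-L1 expression will be determined by qRT-PCR and/or IHC". The Section 10.2.2 calendar, for the arm without MLA, schedules research blood, lymph nodes and tissue. That arm closed to new patients with Amendment 12, and its enrolled number is not given.

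**When.** Section 9.1.1 has one blood draw within the week before the surgical procedure and another "No more than 3 days prior to the first dose of MK-3475", followed by draws at doses 2, 4, 6, 9, 18 and 36 and at end of treatment. Section 9.2.1 adds an optional node sample at the procedure and again six weeks later. Under Section 9.3.1, tumor tissue comes from debulking or from a biopsy, including the biopsy done during MLA.

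**The objectives.** Section 2.2, objectives 4 and 5, link the markers to PFS and OS in phase II without naming an arm. Objectives 2 and 3 do name MLA.

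**The models.** Section 15.2 has two such sentences. The first reads "Cox proportional hazard model will be used to determine the relationship between intratumoral expression of PD-L1, the frequency of glioma cell-specific cytotoxic T cells"; its outcomes are both survival endpoints. The second reads "Cox proportional hazard model will be used to investigate the relationship between PD-1-dependent biomarkers in glioma cell-specific T cells and PFS and OS". Neither sentence mentions a treatment term, stratification, restriction to one arm, or the draw that supplies the marker value. The same section still covers both arms elsewhere: "Two-group t-test will be used to compare the anti-glioma immune response before and after MK-3475 with or without MLA".

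**The arm difference.** Section 15.4: "This analysis showed significant differences in PFS and survival probabilities between the MK-3475 + MLA group and the MK-3475 alone group".

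**The concern.** Section 1.5 expects MLA to promote immune activation. Section 15.4 reports longer PFS and survival with MLA. On the plan's own premises, treatment group is therefore related both to a T-cell marker measured after MLA and to the outcome. A Cox model fitted to both arms without treatment group assigns part of the arm difference to the marker. MLA can affect outcome in other ways, including direct cytoreduction (Section 1.2), and the between-arm contrast cannot separate these from the marker.

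At stake are secondary objectives 4 and 5. A marker unrelated to outcome within either arm would be reported as associated with PFS or OS more often than the nominal rate allows, and the estimate for a marker with a real effect would be contaminated in the same way.

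**Working it through.** The plan states no power or error rate for these models, so there is no figure to reproduce. The check asks how often a marker with no within-arm effect is declared significant.

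**Inputs from the documents**
- MK-3475 + MLA phase II patients: 10 at the interim (Section 15.4) + 20 further evaluable (Section 1.7) = 30.
- Median PFS 2.73 months (alone) and 5.49 months (with MLA): hazard ratio 2.73/5.49 = 0.50.
- Median OS 4.77 months (alone).

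**Assumptions not in the documents**
- Monotherapy patients: 3, 6, 10 or 15.
- Median OS with MLA: about 12 months. Section 15.4 calls the median not estimable but gives 50.0% survival at 12 months. Hazard ratio 4.77/12 = 0.40.
- MLA raises the marker by 1 or 1.5 SD; a shift of 0 stands for a marker taken before MLA.
- Exponential times; censoring uniform over 6 to 26 months.

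**Test.** Cox score test at two-sided 5%: Z = U/√V, where U = Σ(mᵢ − m̄ᵢ) over events, m̄ᵢ is the mean marker in the risk set at event i, and V is the sum of the risk-set variances. In the stratified version the risk sets contain only patients of the same arm. 20,000 simulated trials per setting; simulation error is about 0.2 to 0.3 percentage points.

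**False-positive rate without treatment group, 30 MK-3475 + MLA patients**

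| Monotherapy n | PFS, 1 SD | PFS, 1.5 SD | OS, 1 SD | OS, 1.5 SD |
|---|---|---|---|---|
| 3 | 6.2% | 6.8% | 6.6% | 7.8% |
| 6 | 7.2% | 9.8% | 9.0% | 12.8% |
| 10 | 9.6% | 14.0% | 12.5% | 20.1% |
| 15 | 12.6% | 20.1% | 16.7% | 26.8% |

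Stratified by arm, every setting gives about 5-6%. With a shift of 0, the unstratified test also stays at about 5-6%.

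**Which samples are exposed.** The mechanism needs a measurement that MLA could have changed.
- Exposed: the pre-dose-1 draw, all later draws, and the six-week node.
- Not exposed: the pre-procedure draw, tissue from debulking (Section 5.0 places MLA at least 3 weeks afterwards), and tissue from the biopsy at MLA. Intratumoral PD-L1 is therefore largely outside it.

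**What stratifying costs in power.** Take a real marker effect, HR 0.6 per SD.
- Marker does not differ by arm, 10 monotherapy patients: about 0.73 unstratified, 0.72 stratified, equal within simulation error.
- The whole PFS difference acts through the marker. The shift this needs is ln(5.49/2.73)/(−ln 0.6) = 0.699/0.511 = 1.37 SD. Power falls from about 0.81-0.82 to 0.69 with 6 monotherapy patients, and from 0.89 to 0.74 with 10.

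**The case against.** The strongest reply has four parts.

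1. *The plan never says that the arms are pooled.* True. But objectives 4 and 5 carry no arm restriction, both arms are sampled, and Section 15.2 still speaks of patients with or without MLA. Fitting the model to all sampled patients is the natural reading, and nothing in the text prevents it.

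2. *Some markers cannot be affected.* This stands for pre-procedure blood and for tissue. It does not clear the later draws, which are most of those scheduled, and Section 15.2 does not say which draw is used.

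3. *If the T-cell response is how MLA works, the pooled association is not spurious.* This stands as a limit on the conclusion. A reader might infer that any T-cell marker raised by MLA will look prognostic solely because of the arm difference. The documents do not support that: the false-positive rate rises but stays far below certainty, and mediation through T cells cannot be excluded. A true mediator should, however, also relate to outcome within an arm, where the stratified model can still detect it.

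4. *Stratifying costs power.* It does if MLA acts through the marker. What is given up is the between-arm contrast, which cannot tell the marker from MLA's other effects.

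A reader might also infer that the bias always runs in the direction the trial hopes for. Objective 5 seeks markers that correlate negatively with T-cell frequency, PFS and OS, and nothing in the documents says that MLA raises those markers.

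**Conclusion.** The concern holds for markers measured after MLA. As written, the models leave out a factor that the plan itself links to both marker and outcome. Under the stated assumptions, the false-positive rate at a nominal 5% is about 6-20% for PFS and 6-27% for OS, against about 5-6% when stratified. The inflation is slight with 3 monotherapy patients and largest with 15 and a 1.5 SD shift; the monotherapy number, the marker shift and the median OS with MLA are all assumed. These are secondary correlative analyses and the primary PFS analysis is untouched, but the plan should be changed, because stratification removes the bias and uses a variable already recorded.

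**What to change.** In Section 15.2:
- Stratify the biomarker Cox models for PFS and OS by treatment group (MK-3475 alone vs MK-3475 + MLA).
- State which sampling time supplies each marker.
- Report the estimate in MK-3475 + MLA patients alone as a sensitivity analysis.

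The cost is a few sentences and no new data. There is no material loss of power if the marker does not differ by arm. If MLA acts through the marker, the stratified test is weaker, as in the illustrative case above (about 0.69-0.74 instead of 0.82-0.89); the plan should acknowledge this.
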